4.2 INCLUSION CRITERIA

For inclusion in the study, participants will fulfil the following criteria:

- Aged ≥ 18 years
- Clinical diagnosis of type 1 myocardial infarction within 12 weeks
- In the opinion of the attending clinician requires dual anti-platelet therapy with aspirin and a P2Y12 receptor antagonist.
- Resident in the country of recruitment with their unique health identifier
- The attending clinician has equipoise regarding the duration of therapy
- Provision of informed consent

4.3 EXCLUSION CRITERIA

Participants will not enter the study if any of the following exclusion criteria are fulfilled:

- Clear indication for specific duration of dual anti-platelet therapy
- Type 2 myocardial infarction
- Contraindication to aspirin or P2Y12 receptor antagonist.
- Non-resident in the country of recruitment
- Previous recruitment into the trial
- Inability or unwilling to give informed consent

4.4 CO-ENROLMENT

Given the simplicity of the intervention, the minimal burden on the trial participant and the current diversity of clinical practice, it is anticipated that co-enrolment in

other studies will be permitted for the majority of patients except where this would undermine the primary end-points of the trials. Co-enrolment in observational studies will be permitted. Co-enrolment in interventional trials will require agreement between the Chief Investigators and Trial Steering Committees of the respective trials as well as the trials Sponsors and will be performed in accordance with the ACCORD guidelines for co-enrolment GL001.

5 PARTICIPANT SELECTION AND ENROLMENT

5.1 IDENTIFYING PARTICIPANTS

Patients will be identified and recruited from the cardiology and general medical hospital wards. All patients will be approached for study recruitment by their usual care team including appropriately trained members of the research team to whom this task has been delegated (this is not restricted to clinicians). Patients will be provided with a Patient Information Sheet and given an opportunity to ask questions about participation in the trial.

5.2 CONSENTING PARTICIPANTS

After an appropriate period of time, patients willing to participate in the study will be asked to provide written informed consent by the patient's usual care team or appropriately trained members of the research team to whom this task has been delegated (this is not restricted to clinicians). Written informed consent will be obtained before any study related procedures are performed.

5.3 SCREENING FOR ELIGIBILITY

The patient's usual care team or appropriately trained members of the research team to whom this task has been delegated (this is not restricted to clinicians) will identify potential participants and confirm and document eligibility. This will be based on routinely collected clinical data and review of clinical records.

5.4 INELIGIBLE AND NON-RECRUITED PARTICIPANTS

Ineligible and non-recruited patients will receive standard medical care. Characteristics and profile of these patients will be determined from routinely collected electronic health record data so a screening log will not be required.

5.5 RANDOMISATION

5.5.1 Randomisation Procedures

A web-based computer-generated randomisation process will be used to ensure allocation concealment and reduce bias. The randomisation system will be provided by ECTU and patients will be randomised using their unique health identifier to prevent inadvertent duplicate randomisation. International sites will use their own randomisation system which will be described in their country specific protocol. Randomisation will be by permuted-block with a level of stratification for

each of the following groups of patients: (i) conservative non-invasive strategy (invasive coronary angiography is not planned), (ii) invasive coronary angiography is planned but has not yet occurred, (iii) an invasive coronary angiogram has been performed and the patient has been referred or undergone CABG surgery, (iv) an invasive coronary angiogram has been performed and the patient has had at least one drug eluting stent implanted, (v) an invasive coronary angiogram has been performed and the patient has had only bare metal stents implanted (this group will also include patients who have had balloon angioplasty only performed without stent implantation), (vi) an invasive coronary angiogram has been performed and the patient is to receive medical management only.

Block size will be randomly determined, and each block will contain both treatments in a 1:1 ratio.

5.5.2 Treatment Allocation

Patients will be randomised 1:1 to 3 or 12 months of dual anti-platelet therapy. Dual anti-platelet therapy will consist of aspirin plus a P2Y12 receptor antagonist (clopidogrel, ticagrelor or prasugrel) chosen by the attending clinician. The participant will be provided with a study card detailing the duration of therapy that they have been randomised to.

5.5.3 Methods to Ensure Blinding

This is an open-label trial and there will be no masking of treatment allocation or need for unblinding.

5.5.4 Discontinuation of the Investigational Medicinal Product

Changes to the duration of therapy will be discouraged but can be changed at the discretion of the attending clinician. Given that discontinuation of dual anti-platelet therapy can be inconsistent [Bueno et al, 2016], the patient's General Practitioner and Consultant Cardiologist will be contacted with a prompt to discontinue the dual antiplatelet therapy before the randomised duration of therapy ends.

5.6 WITHDRAWAL OF STUDY PARTICIPANTS

Participants are free to withdraw from the study at any point or a participant may be withdrawn by the attending clinician. If a participant wishes to withdraw they will need to contact their local research team who will document the nature and primary reason for withdrawal, if possible. The contact details for the local site will be provided on a study card. Unless the participant specifically withdraws consent any data collected up to the point of withdrawal will be retained and analysed and data will continue to be collected remotely from the participant's medical notes and via data linkage.

Participants who withdraw or are withdrawn from the study will not be replaced.

6 INVESTIGATIONAL MEDICINAL PRODUCTS

6.1. STUDY DRUGS

There are four IMPs being used in the study: aspirin (75 mg tablet), clopidogrel (75 mg tablet), ticagrelor (90 mg tablet) and prasugrel (10 mg tablet or 5 mg tablet if participant is over 75 years or weight <60 kg).

All IMPs have marketing authorisations for the condition (acute coronary syndrome) under investigation here. As several brands of both clopidogrel and aspirin are marketed in the UK, the IMPs are defined by the active substance only. All authorised brands may be used and pharmacies may provide the brand of drug which is available to them.

All drugs will be stored, used and prescribed by an authorised healthcare professional according to local clinical practice guidelines.

The Summary of Product Characteristics (SPCs) for all 4 IMPs are provided in a separate document which has been signed and verified by the CI and the Sponsor.

6.2. PARTICIPANT COMPLIANCE

Compliance with the randomised duration of therapy will be assessed using routine collected prescribing data, where possible, for the purposes of the study outcomes. Non-compliance will not be recorded or reported to the Sponsor.

6.3. OTHER MEDICATIONS

6.3.1 Prohibited Medications

There are no prohibited medications in this study. Patients will be treated as per standard care.

7 STUDY ASSESSMENTS

7.1 DATA COLLECTION AND OUTCOME ASSESSMENTS

Baseline patient characteristics, past medical history and medication use will be obtained from the randomisation database and data linkage from the participant's electronic health records.

Outcome measures for patients recruited in Scotland will be obtained through the Farr Institute in collaboration with the electronic Data Research and Innovation Service (eDRIS) and the General Register Office as we have successfully achieved with the SCOT-HEART [SCOT-HEART, 2015; Williams et al, 2016] and HighSTEACS [Shah et al, 2015a; Shah et al, 2015b] trials (Tables 2 and 3). We will capture all hospital admission events and will have access to clinical records and imaging as required through NHS Safe Havens. Outcome measures for patients recruited in England will be obtained through NHS Digital. We will record the following safety endpoints: all-cause death, non-cardiovascular death, fatal bleeding, major bleeding (including gastrointestinal and intracranial haemorrhage), hospitalization for bleeding (all ICD-10 coded), as well as blood transfusions, where possible). The bleeding data will be used to classify bleeding events using the standardized bleeding definition for cardiovascular clinical trials as defined by the Bleeding Academic Research Consortium (BARC) [Mehran et al, 2011]. We will record the following efficacy endpoints: all-cause death, cardiovascular (cardiac and non-cardiac) death, myocardial infarction (non-fatal and fatal) [Thygesen et al, 2012], stroke (non-fatal and fatal; thrombotic and haemorrhagic), coronary revascularisation (percutaneous coronary intervention and coronary artery bypass graft surgery), and stent thrombosis.

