SD	Standard deviation
SOP	Standard operating procedure
TCL	Total cholesterol
TRE	Trusted research environment
TRI	Triglycerides
UK	United Kingdom

1. Introduction

This document details the criteria to be used for the definitions of the analysis populations and the statistical methodology for analysis of the Dual-ACS trial, a prospective multicentre national open-label randomised controlled trial comparing the duration of dual antiplatelet therapy. The aim is to randomise 18,318 patients with type I myocardial infarction (MI) to 12 or 3 months of dual antiplatelet therapy in a 1:1 ratio. Randomisation is by permuted-blocks with a level of stratification for each of the following groups of patients:

- (i) conservative non-invasive strategy (invasive coronary angiography is not planned),
- (ii) invasive coronary angiography is planned but has not yet occurred,
- (iii) an invasive coronary angiogram has been performed and the patient has been referred or undergone coronary artery bypass grafting (CABG) surgery,
- (iv) an invasive coronary angiogram has been performed and the patient has had at least one drug eluting stent implanted,
- (v) an invasive coronary angiogram has been performed and the patient has had only bare metal stents implanted,
- (vi) an invasive coronary angiogram has been performed and the patient is to receive medical management only.

Recruitment in the United Kingdom (UK) was halted after 4,576 patients because the funder felt the trial was no longer deliverable due to the challenging environment of the COVID-19 pandemic. The statistical analysis will include the patients recruited in the UK and as many international patients who have completed 15 months follow-up at the time of analysis.

This document has been compiled according to the Edinburgh Clinical Trials Unit (ECTU) standard operating procedure (SOP) “ECTU_SOP_ST_04 Statistical Analysis Plans v7.0” and has been written based on information contained in the study protocol version 6.0, dated 22nd July 2022.

2. Statistical Methods section from the protocol

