4.1 ITT analysis population

The ITT analysis population will include patients who have been randomised into the Dual ACS trial in the UK and New Zealand (NZ) and for whom outcome data are available. Those who subsequently became ineligible after a diagnosis other than Type 1 myocardial infarction (MI) and withdrawn from the trial will be excluded¹.

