Appendix C

Outcomes defined used the following codes and positions specified below following the date of index MI unless otherwise specified. If the code is not identified in any admissions/deaths then they will be assumed to not have the outcome of interest.

Data sources

Scotland: SMR00 / SMR01 / NRS Deaths / Prescribing Information System / Scottish Blood Transfusion Database

England: Hospital Episode Statistics / Civil Registrations of Death / Medicines dispensed in Primary Care (NHSBSA data)

Outcome	Code (ICD-10 , OPCS4)
All-cause mortality	Any record of death.
Non-cardiovascular death (including fatal bleeding) and major non-fatal bleeding	
Death due to a non-cardiovascular cause
 
Primary position for cause of death
 
Ax, Bx, Cx, Dx Ex, Fx , Gx , Hx , Jx, Kx , Lx , Mx , Nx , Ox , Px , Qx , Rx , Sx , Tx , Ux , Vx , Xx , Yx , Zx.
 
OR
 
Hospitalisation for bleeding
 
Primary or first secondary position
 
I60x, I61x, I62x, S06.4x, S06.5x, S06.6x, K92.0x, K92.1x, K 92.2x, I85.0x, I98.3x, K22.6x, K25.0x, K25.2x, K25.4x, K25.6x, K26.0x, K26.2x, K26.4x, K26.6x, K27.0x, K27.2x, K27.4x, K27.6x, K28.0x, K28.2x, K28.4x, K28.6x, K29.0x, K62.5x, K66.1x, R58x, I23.0x, I31.2x, I69.0x, I69.1x, I69.2x, H21x, H35.6x, H31.3x, H43.1x, H44.8x, H45.0x, R04.0x, R04.1x, R04.2x, R04.8x, R04.9x, T81.0x, D62x, N83.7x, N93.8x , N93.9x, O03.1x, O03.6x, O04.1x, O04.6x, O05.1x, O05.6x, O06.1x, O06.6x, O20.8x, O20.9x, O46x , O67x, O07.1x, O07.6x, O08.1x, O71.7x , O72.0x , O72.1x , O72.2x , O90.2x , P26.1x , R31x , M25.0x.
 
OR

	
Primary procedure position (OPSC4)
 
E05x , E058x , E059x , F162x , D041x , E203x , F365x , G523x , H212x , H531x , K681x , P093x , P271x , T301x , Y221x , T032x , Y221x , T032x , Y321x , V032x , A052x , A053x , A054x , A103x , A401x , A411x

Non-cardiovascular death (including fatal bleeding)	
Primary cause of death
 
Ax , Bx , Cx , Dx , Ex , Fx , Gx , Hx , Jx , Kx , Lx , Mx , Nx , Ox , Px , Qx , Rx , Sx , Tx , Ux , Vx , Xx , Yx , Zx

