Myocardial infarction (fatal and non- fatal)	
Myocardial infarction after the Index Admission Discharge Date
 
Primary or first secondary position
 
I21x, I22x
 
OR
 
Death due to myocardial infarction
 
Primary cause of death
 
I21x, I22x

Stent thrombosis	
Stent thrombosis
 
Primary or first secondary position
 
T82.8x

Coronary revascularisation	
Coronary revascularisation after the Index Admission Discharge Date
 
Primary procedure position (OPCS4)

	K40x, K41x, K42x, K43x, K44x, K45x, K46x, K47x, K48x, K49x, K50x, K75x.
Thrombotic stroke	
Ischaemic stroke
 
Primary or first secondary position
 
I63x
 
OR
 
Death due to ischaemic stroke
 
Primary cause of death
 
I63x

Blood transfusion	Any record of transfusion
Iron therapy	
Prescribed Iron Therapy
 
Approved drug names: FERROUS SULPHATE, FERROUS FUMARATE, FERROUS GLUCONATE, FERRIC MALTOL, FERROUS CALCIUM CITRATE, FERROUS GLYCINE SULFATE, IRON CARBOXYMALTOSE, SODIUM FEREDETATE, IRON CARBOXYMALTOSE, IRON DEXTRAN, IRON SUCROSE, VENOFER, FERINJECT

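### SAP Appendix C scores stent thrombosis from one code, requires no coronary stent and does not exclude the index admission, so the endpoint is not specific to stent thrombosis

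*Protocol*

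**What the plan says.** Stent thrombosis is a secondary efficacy endpoint in Protocol Table 3 and SAP 4.6. Protocol 7.1 ends its list of efficacy endpoints with "coronary revascularisation (percutaneous coronary intervention and coronary artery bypass graft surgery), and stent thrombosis" and defines neither the event nor how it is confirmed.

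The working definition is one row of SAP Appendix C: T82.8x in "Primary or first secondary position". Three general rules apply to it:

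- **Time window.** Appendix C codes count "following the date of index MI unless otherwise specified". The stent thrombosis row specifies nothing further. The revascularisation row does, as "Coronary revascularisation after the Index Admission Discharge Date", and the two rows that count recurrent infarction carry the same condition.
- **Absent code.** "If the code is not identified in any admissions/deaths then they will be assumed to not have the outcome of interest".
- **Population.** SAP 4.6 sends the analysis to section 4.5, in the ITT population of section 4.1. That population takes in every management stratum. One is described by "the patient has had at least one drug eluting stent implanted"; others are conservative management, bypass surgery, and patients for whom "the patient is to receive medical management only".

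The any-position sensitivity analysis in SAP 4.6.1 is limited to safety outcomes, so it does not reach this endpoint.

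**The concern.** The row contains nothing that ties a coded event to a coronary stent. A participant managed conservatively or by bypass, with no stent at all, is in the analysis and would score an event if the code appeared. A code recorded during the index admission would also count, although at that time both arms are on the same treatment.

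This matters because Protocol 1.1 names stent thrombosis as a particular hazard of moving from dual to single therapy. It is one of the ischaemic costs to be weighed against less bleeding with 3 months. If the coded events include some that allocation cannot influence, the estimated ratio moves towards 1 and the comparison looks more reassuring than it should. Precision is already limited: UK recruitment stopped at 4,576 of 18,318 planned (4,576 / 18,318 = 25.0%).

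**Working it through.** **No figure to reproduce.** Neither document gives a rate, effect size or power for stent thrombosis, so the check is first of the text and then an illustration.

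**Step 1: compare the Appendix C rows.**

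| Row | After index discharge? | Cause-of-death part? |
|---|---|---|
| Myocardial infarction | Yes | Yes |
| Coronary revascularisation | Yes | No |
| Stent thrombosis | No | No |

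If the general time rule already excluded the index admission, the extra condition in the first two rows would be redundant. The natural reading is that index-admission codes count for stent thrombosis.

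**Step 2: can allocation affect those events?** SAP 4.5.2 says that both groups receive the same treatment for the first 3 months and that no difference is expected then apart from chance. Index-admission events are therefore expected to be neutral between arms. Protocol 4.2 also allows entry up to 12 weeks after the infarction, so some codes could precede randomisation.

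**Step 3: who can be counted?** Conservative, medical-only and bypass strata are in the ITT population. Stratum alone does not show who has a stent. Protocol 5.5.1 places balloon-only patients in the bare-metal stratum, stratum ii patients may be stented after randomisation, and some patients in unstented strata may have older stents.

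**Step 4: is there any safeguard?** Quality-control item 4 in SAP section 5 checks that the data codes map to the SAP, not that the SAP code represents the endpoint. Protocol 7.1 foresees access to records and imaging, but the SAP plans no such confirmation for this endpoint.

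**Step 5: illustrate the dilution.** Let q be the share of the 12-month arm's coded events that are true stent thrombosis, and suppose the rest are unaffected by allocation. For uncommon events,

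observed ratio = q × true ratio + (1 − q) × 1.

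For example, 0.5 × 1.5 + 0.5 × 1 = 1.25. Events needed for 80% power (two-sided 5%, 1:1, Schoenfeld) = 4 × (1.960 + 0.842)² / (ln ratio)². Both q and the true ratio are assumptions.

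| q | True 1.5: observed | Events needed | True 2.0: observed | Events needed |
|---|---|---|---|---|
| 100% | 1.50 | 191 | 2.00 | 66 |
| 75% | 1.375 | 310 | 1.75 | 101 |
| 50% | 1.25 | 631 | 1.50 | 191 |
| 25% | 1.125 | 2,264 | 1.25 | 631 |

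The share must be that of the 12-month arm. If 75%, 50% or 25% were shares p of both arms pooled, then with a true ratio of 1.5 the ratio of other to true events in the 12-month arm is (1 + 1.5)(1 − p) / (2p) = 0.417, 1.25 or 3.75. Then q = 1 / (1 + that ratio) = 0.706, 0.444 or 0.211, and the observed ratio is about 1.35, 1.22 or 1.11.

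**The case against.** **The code's content.** A reader might infer that T82.8x is a residual device-complication code that takes in stenosis, haemorrhage and devices other than stents, so that the endpoint does not measure stent thrombosis at all. The documents print only the code, never its label or contents, so they do not support this. They also do not support a reading that any such code counts, because position is limited to primary or first secondary. For the same reason there is no basis here for adding a bleeding component with its own hazard ratio to the dilution arithmetic.

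**Hidden harm.** A reader might also infer that the harm of stopping early is concealed. That goes too far. A thrombosis that presents as infarction or leads to a repeat procedure, coded in the required position, still counts under those separate endpoints. Protocol 1.1 reports rebound whenever therapy stops, and follow-up to 15 months from the infarction covers the stopping point of both arms. Secondary outcomes are read by effect size and interval.

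**Unstented participants.** Those who have no event lower the absolute rate but do not bias the hazard ratio, since randomisation is stratified by management group and the model adjusts for it. This stands. The concern is with events wrongly counted.

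**Landmark analysis.** If SAP 4.6 is read as carrying over the 3-month landmark of SAP 4.5.2, that would reduce the weight of early events. It would not change the definition or add a stent requirement.

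What remains after these points is the missing stent requirement, the missing discharge condition, the all-patient population and the absence of any check on the definition.

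**Conclusion.** The concern holds as a lack of specificity. The stent thrombosis row can count events in participants with no coronary stent and events in the index admission, when the arms do not yet differ, and nothing planned would show how often this happens.

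The direction, towards a hazard ratio of 1, rests on the assumption that the extra events are unaffected by allocation. SAP 4.5.2 supports this for index-admission events. For events in unstented participants it is an assumption. The size cannot be derived from the documents. The 1.38, 1.25 and 1.13 for a true ratio of 1.5 are illustrative and hold only if the shares are those of the 12-month arm.

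A secondary endpoint is affected. All-cause mortality, the primary endpoint, is not.

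**What to change.** Amend the stent thrombosis row of Appendix C and the matching analysis text:

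1. Count T82.8x only where a coronary stent is recorded before the event, from the randomisation record or linked procedure codes (Appendix A labels K75.1 to K75.4 as stent insertions). Include earlier stents, and do not rely on stratum alone. Name equivalent codes for New Zealand, since the appendices list only Scottish and English sources.
2. Count only events after the index admission discharge date, as for infarction and revascularisation.
3. Add an analysis restricted to participants with a coronary stent at randomisation. This subgroup is fixed before allocation, so the randomised comparison is kept.
4. Report two sensitivity analyses: the unrestricted T82.8x count, labelled by the code's own heading once the code list has been checked; and a stricter version that also needs I21x/I22x or K49x/K50x/K75x in the same admission.

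The companion-code rule belongs in the sensitivity analyses. Without item 2, an index admission coded I21x would meet it automatically. A repeat procedure done for another reason would meet it too, and a true thrombosis coded without either would be lost.

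The cost is a changed row and modest programming on data already linked in the UK, plus the New Zealand code mapping. The main definition will have fewer events and a wider interval.

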7.2 COMPLIANCE

Compliance with the duration of therapy will be undertaken by record linkage with community-dispensed prescriptions and/or national registries, where possible.

